2 STUDY DESCRIPTION

2.1 Study Design

This is an open-label, randomized, parallel-group, single-dose, biocomparability study in healthy subjects. Due to a number of significant deviations that occurred at Site 2, 30 replacement subjects will be dosed. The data from the 30 subjects who were enrolled and dosed at Site 2 will

not be included in the analysis, and the data from the 30 replacement subjects to be dosed will be included in the analysis.

The initial plan was to dose approximately 146 subjects (approximately 73 in each treatment group) in order to complete a minimum of 67 subjects per treatment group. Given the protocol deviations at Site 2, the number of subjects dosed in this study has increased to approximately 176 in order to ensure adequate sample size for the analysis for the primary objective. Subjects will undergo screening evaluations to determine eligibility within 28 days prior to dosing on Day 1. To allow for possible dropouts, an adequate number of subjects will need to meet the inclusion/exclusion criteria at screening so that approximately 88 subjects (73 initial planned and 15 replacements) per treatment group will be dosed on Day 1.

Subjects will enter the study site on Day -1 and remain confined until completion of the Hour 72 PK sample collection on Day 4. On Day 1, subjects will be randomly assigned within stratified weight categories in a 1:1 ratio to receive either Process E belatacept or Process C belatacept, 10 mg/kg, IV infused over 30 minutes. Subjects will return to the study site for PK blood sample collections after they are furloughed on Day 4 from the study site. Blood samples will be collected through Day 57 (approximately 5-6 half-lives) for PK analysis and through Day 71 (approximately 7-8 half-lives) for assessment of immunogenicity when drug concentrations are low and unlikely to interfere with analysis of anti-drug antibodies.

The PK and immunogenicity serum samples will be collected at selected times throughout the study. Serum samples for immunogenicity will be obtained prior to dosing and after dosing on Days 29, 43, 57, and 71.

The study design schematic is presented in Figure 2.1-1.

Figure 2.1-1: Study Design Schematic

Days -28 to -1	Day 1		Day 4	Days 5 to 71	Day 71
S, E	R ^a	10 mg/kg IV Process E belatacept OR 10 mg/kg IV Process C belatacept Serial PK sampling	Furlough After Hour 72 PK sample	PK ^b : Days 8, 15, 22, 29, 36, 43, 57 IMG: Days 29, 43, 57, 71	Discharge ^c

Abbreviations: E = enrollment; IMG = immunogenicity; IV = intravenous; PK = pharmacokinetic; R = randomization; S = screening.

^a Subjects randomly assigned within stratified weight categories in a 1:1 ratio.

^b Subjects will return to the study site for collection of a single PK sample.

^c Evaluations performed prior to study discharge, or for subjects who are prematurely discontinued.

Physical examinations, vital sign measurements, 12-lead ECGs, and clinical laboratory evaluations will be performed at selected times throughout the study. Subjects will be closely monitored for AEs throughout the study. Approximately 200 mL of blood will be drawn from each subject during the study.

The approximate duration of the study is a 28-day screening period, 71 study days per subject for a total of up to 99 days.

Subjects who seroconvert and continue to have a high titer at study discharge that is considered to be significantly increased versus baseline will be asked to return for follow-up assessment(s) for anti-belatacept antibodies approximately every 4 months until their titers and/or sero-status are judged to be stable by the investigator.

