Amendment 02	27-Sep-2016	The purpose of this protocol amendment is to add 30 replacement subjects who will be dosed. Audit and monitoring visits revealed major protocol deviations at Site 2. Due to the number and significance of these deviations, BMS does not believe that the data generated at this site should be included in the primary analysis.
Revised Protocol 01	06-Jan-2016	Incorporates Amendment 01 and Administrative Letter 01
Amendment 01	06-Jan-2016	The purpose of this protocol amendment is to fulfill the United States Food and Drug Administration (FDA) request to monitor subjects until titer and/or sero-status are judged to be stable by the investigator and to include an additional immunogenicity sample in the protocol. During review of this protocol for belatacept, the FDA requested that at the completion of the Day 71 visit, subjects that seroconvert will be asked to continue to participate until judged to be stable by the investigator and to add an immunogenicity sample on Day 15. In accordance with this, subjects who seroconvert will be asked to return for a visit approximately every 4 months after Day 71. These changes will apply to all current and future subjects after this amendment is approved.
Administrative Letter	06-Nov-2015	The purpose of this administrative letter was to clarify the units of measure for study drug dosage in Section 4 of the protocol, to clarify the subject numbers if replacement subjects are used in Section 4.4 , and to update an inconsistency in Table 5.1-2 regarding the length of collection for nonserious adverse events (AEs) based on study duration. Both Treatment A and Treatment B will be dosed as 10 mg/kg, replacement subjects will be assigned the original subject's number plus 500, and all nonserious AEs will be collected through Day 71.
Original Protocol	14-Sep-2015	Not applicable

SYNOPSIS

Clinical Protocol IM103349

Protocol Title: A Randomized, Open-label, Parallel-group, Single-dose, Biocomparability Study of the Pharmacokinetics of Belatacept Drug Products Using Active Pharmaceutical Ingredient Manufactured by Process E Relative to Active Pharmaceutical Ingredient Manufactured by Process C in Healthy Subjects

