Subjects will enter the study site on Day -1 and remain confined until completion of the Hour 72 PK sample collection on Day 4. On Day 1, subjects will be randomly assigned within stratified weight categories in a 1:1 ratio to receive either Process E belatacept or Process C belatacept 10 mg/kg, IV infused over 30 minutes. Subjects will return to the study site for PK blood sample collections after they are furloughed on Day 4 from the study site.

Blood samples for measurement of serum belatacept concentrations and immunogenicity will be obtained according to the schedule in [Table 5.5.1-1](#).

Blood samples for immunogenicity assessments will be drawn prior to dosing and after dosing on Days 15, 29, 43, 57, and 71.

Subjects will be closely monitored for adverse events (AEs) throughout the study. Clinical laboratory tests, vital sign measurements, 12-lead electrocardiogram (ECG) measurements, and physical examinations will be performed at selected times following dosing. The approximate duration of the study is 99 days, including a 28-day screening period and a 71-day study period.

Subjects who seroconvert and continue to have a high titer at study discharge that is considered to be significantly increased versus baseline will be asked to return for follow-up assessment(s) for anti-belatacept antibodies approximately every 4 months until their titers and/or sero-status are judged to be stable by the investigator.

Subjects will undergo study procedures according to the study design schematic (Figure 1).

Figure 1: **Study Design Schematic**

Days -28 to -1		Day 1	Day 4	Days 5 to 71	Day 71
S, E	R ^a	10 mg/kg IV Process E belatacept OR 10 mg/kg IV Process C belatacept Serial PK sampling	Furlough after Hour 72 PK sample	PK ^b : Days 8, 15, 22, 29, 36, 43, 57 IMG: Days 15, 29, 43, 57, 71	Discharge ^c

Abbreviations: E = enrollment; IMG = immunogenicity; IV = intravenous; PK = pharmacokinetic; R = randomization; S = screening.

a Subjects randomly assigned within stratified weight categories in a 1:1 ratio.

b Subjects will return to the study site for collection of a single PK sample.

c Evaluations performed prior to study discharge, or for subjects who are prematurely discontinued.

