3. INVESTIGATIONAL PLAN

3.1 Study Design and Duration

This is an open-label, randomized, parallel-group, single-dose, biocomparability study in healthy subjects. Due to a number of significant deviations that occurred at Site 2, 30 replacement subjects will be dosed. [Section 4.4](#) allows for replacement of subjects at sponsor discretion. The data from the 30 subjects who were enrolled and dosed at Site 2 will not be included in the primary analysis, and the data from the 30 replacement subjects to be dosed will be used for the primary analysis.

The initial plan was to dose approximately 146 subjects (approximately 73 in each cohort) in order to complete a minimum of 67 subjects per cohort. Given the protocol deviations at Site 2, the number of subjects dosed in this study has now increased to approximately 176 in order to ensure adequate sample size for the primary analysis. Subjects will undergo screening evaluations to determine eligibility within 28 days prior to dosing on Day 1. To allow for possible dropouts, an adequate number of subjects will need to meet the inclusion/exclusion criteria at screening so that 73 subjects per arm will be dosed on Day 1.

Subjects will enter the study site on Day -1 and remain confined until completion of the Hour 72 PK sample collection on Day 4. On Day 1, subjects will be randomly assigned within stratified weight categories in a 1:1 ratio to receive either Process E belatacept or Process C belatacept, 10 mg/kg, IV infused over 30 minutes. Subjects will return to the study site for PK blood sample collections after they are furloughed on Day 4 from the study site. Blood samples will be collected through Day 57 (approximately 5-6 half-lives) for PK analysis and through Day 71 (approximately 7-8 half-lives) for assessment of immunogenicity when drug concentrations are low and unlikely to interfere with analysis of anti-drug antibodies.

The PK and immunogenicity blood sample schedule is shown in [Table 5.5.1-1](#). Blood samples for immunogenicity will be obtained prior to dosing and after dosing on Days 15, 29, 43, 57, and 71.

The study design schematic is presented in [Figure 3.1-1](#).

Figure 3.1-1: Study Design Schematic

Days -28 to -1		Day 1	Day 4	Days 5 to 71	Day 71
S, E	R ^a	10 mg/kg IV Process E belatacept OR 10 mg/kg IV Process C belatacept Serial PK sampling	Furlough After Hour 72 PK sample	PK ^b : Days 8, 15, 22, 29, 36, 43, 57 IMG: Days 15, 29, 43, 57, 71	Discharge ^c

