2.4 Protocol Amendments

This analysis plan reflects all protocol amendments through Amendment #2, dated 27-Sep-2016.

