7.7 Pharmacokinetics

The PK population will be used for all listings. Evaluable PK population will be used for summary statistics and statistical analyses. Analysis will include all analyte data in the PK dataset for belatacept.

Subject serum concentration-time data will be listed and summarized by treatment and nominal collection time for belatacept. Details of T-HALF derivation and the harmonic mean of terminal slope by treatment will also be presented. Plots of individual serum concentration profiles over time will be provided. Overlay of individual serum concentration profiles over time will be provided by treatment. Plots of mean (+SD) serum concentration profiles versus time will be presented for belatacept, and both treatments will be superimposed on the same plot.

All individual PK parameters will be listed for belatacept including any exclusions and reasons for exclusion from summaries. Summary statistics will be tabulated for each PK parameter by treatment. Geometric means and CV% will be presented for Cmax, AUC(0-T), AUC(INF), CLT, and Vss. Medians and ranges will be presented for Tmax. Arithmetic mean and standard deviation will be presented for T-HALF. Decimal place specifications for summary statistics are described in Section 7.10.

Separately by antibody status (negative antibody status with respect to baseline as defined in Section 7.9) and overall, a linear fixed effect model with treatment as a fixed effect will be employed. Kenward-Rogers degrees of freedom will be specified in the model. Point estimates and 90% CIs for treatment differences on the log-scale will be exponentiated to obtain point estimates and 90% CIs for the ratios of geometric means on the original scale. A sensitivity analysis comparing the PK between Process E and Process C may be performed by excluding patients who are positive for anti-belatacept antibodies. The following SAS code will be implemented, where A is the Process E belatacept, and B is the Process C belatacept.

Plots of individual Cmax, AUC(0-T) and AUC(INF) combined with corresponding geometric means will be provided versus treatment.

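### Does the SAP drop the Day 15 immunogenicity sample from the antibody analyses?

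*SAP*

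**What the plan says.** The protocol gives five post-dose immunogenicity days. Section 3.1 reads "Blood samples for immunogenicity will be obtained prior to dosing and after dosing on Days 15, 29, 43, 57, and 71". The synopsis, both design schematics, Table 5.1-2 and Table 5.5.1-1 agree. The document history traces Day 15 to Amendment 01 of 06-Jan-2016, in which the FDA asked the sponsor "to add an immunogenicity sample on Day 15". On who is covered it says: "These changes will apply to all current and future subjects after this amendment is approved".

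SAP 2.1 lists four post-dose days in its text, "Serum samples for immunogenicity will be obtained prior to dosing and after dosing on Days 29, 43, 57, and 71", and Figure 2.1-1 repeats them as "IMG: Days 29, 43, 57, 71". SAP 2.4 nevertheless states: "This analysis plan reflects all protocol amendments through Amendment #2, dated 27-Sep-2016".

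Antibody status is used again in SAP 7.7, where the PK model is fitted "Separately by antibody status (negative antibody status with respect to baseline as defined in Section 7.9) and overall". A sensitivity analysis without antibody-positive subjects is optional there and in protocol 8.4.4.

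**The concern.** A SAP that claims to be current with every amendment lists a sampling schedule that predates Amendment 01. The missing time point is one a regulator requested.

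The visit list could matter in two places. The protocol synopsis tabulates positive responses by study day, so a four-day list carried into the table shells would leave out the Day 15 row. SAP 7.7 also runs the treatment comparison in antibody-negative subjects. If status came from the four listed days only, a subject positive on Day 15 alone would be classed as negative. That subject would stay in the antibody-negative comparison and lower the reported incidence.

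Protocol 1.4.4.2 says antibody formation in healthy subjects can reach 100%. The antibody-negative group could therefore be small, and a few misclassified subjects could carry weight in it.

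**Working it through.** No stated figure depends on this point, so the check compares the two schedules and then asks which sections act on them.

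**Schedules**

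| Source | Post-dose immunogenicity days | Count |
|---|---|---|
| Protocol 3.1, synopsis, Tables 5.1-2 and 5.5.1-1 | 15, 29, 43, 57, 71 | 5 |
| SAP 2.1 text and Figure 2.1-1 | 29, 43, 57, 71 | 4 |

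Protocol days minus SAP days leaves Day 15 only; SAP days minus protocol days leaves none. The SAP describes 4/5 = 80% of the post-dose samples.

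**Slip or decision?** Three features point to an incomplete update:
- SAP 2.1 does carry Amendment 01's other change, the follow-up of seroconverters about every 4 months.
- Figure 2.1-1 keeps Day 15 as a PK visit, so only the immunogenicity entry is missing.
- SAP 7.2 says departures from the protocol's planned analysis will be set out in the SAP. No visible text declares one for Day 15.

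**What each section does with the day list**
- *Collection:* the protocol governs, and it includes Day 15.
- *Immunogenicity Analysis Population (SAP 6.3):* one post-baseline result on any day is enough. A subject whose only result is from Day 15 is included, so no subject is lost.
- *Incidence endpoint (SAP 4.6, protocol 8.3.2):* no days are named.
- *Antibody status (SAP 7.7, pointing to 7.9):* the rule is in 7.9, whose body is not visible in the public copy. Whether it uses every post-baseline sample cannot be read either way.
- *Overall PK model (SAP 7.7, protocol 8.4.4):* treatment is the only effect, and the 80% to 125% criterion carries no antibody condition. The primary result is the same whichever days define status.

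**Size**
- Samples: the analysed set is 116 + 30 = 146 subjects, so at most 146 Day 15 samples are involved. This is a ceiling, because subjects already past Day 15 when Amendment 01 was approved may have none. The documents give no dosing dates with which to refine it.
- Antibody-negative subset: this depends on the positivity rate, which the documents do not give. With 2 × 67 = 134 completers and assumed positivity of 50%, 80% or 90%, the group is 134 × 0.50 / 2 = 33.5, 134 × 0.20 / 2 = 13.4 or 134 × 0.10 / 2 = 6.7 per arm. At 13 per arm and a CV of 26%, the Cmax 90% CI half-width is about 0.17 on the log scale, against a limit of ln(1.25) = 0.223. These numbers describe the precision of a small subset. They do not measure any effect of leaving Day 15 out.
- Reclassified subjects: the count needed is of subjects positive on Day 15 and on no later day. The documents give nothing from which to estimate it.

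**The case for a change.** The best case for a change is that the discrepancy is certain, appears in current text in two places and makes the statement in SAP 2.4 untrue of SAP 2.1. Table shells are often built from a SAP's schedule. If the Data Presentation Plan or SAP 7.9 copied the four-day list, the by-day table would lose the time point the FDA asked for, and the antibody-negative PK comparison could be altered. Adding Day 15 costs a few words and needs no new samples. Because some early subjects may have no Day 15 sample, a sentence on its handling would be useful.

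The inconsistency stands in full. The consequence stands only as a conditional, because it needs a copying step that no visible text shows. A programmer working from the collected data will find Day 15 results. The visible population rule admits them, and the protocol's by-day summary gives them a row. A subject with no Day 15 sample is simply missing at that visit, which a by-day incidence table handles in the usual way. Asking for a status rule may be asking for what SAP 7.9 already contains.

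**Conclusion.** The omission is a clerical slip: SAP 2.1 and Figure 2.1-1 keep the immunogenicity days as they stood before Amendment 01. One of five post-dose time points is missing from a design description, with no demonstrable change to any result. The Immunogenicity Analysis Population and the overall AUC(INF) and Cmax comparison are unaffected, and no power, sample size or alpha moves.

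This rests on two assumptions. The first is that Day 15 samples were collected as the protocol requires, for subjects covered by Amendment 01. The second is that SAP 7.9 and the Data Presentation Plan, neither of which can be read here, use the post-baseline results available. If either restricted results to the four listed days, by-day incidence and the antibody-negative PK comparison could shift by an amount the documents do not allow one to compute. The primary conclusion would still not move. No change to the plan is called for.

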2.2 Treatment Assignment

Subjects will be randomly assigned to Process E belatacept or Process C belatacept in 1:1 ratio according to a computer-generated randomization scheme, stratified by weight categories: 60 to < 70 kg, 70 to < 80 kg, 80 to < 90 kg, and 90 to 100 kg. Randomization numbers will be assigned prior to dosing.

2.3 Blinding and Unblinding

This is an open-label study.

2.4 Protocol Amendments

This analysis plan reflects all protocol amendments through Amendment #2, dated 27-Sep-2016.

3 OBJECTIVES

3.1 Primary

The primary objective of this study is to compare the PK of Process E belatacept relative to Process C belatacept following a single-dose IV infusion of 10 mg/kg in healthy subjects.

3.2 Secondary

The secondary objectives are as follows:

- To assess the safety of a single-dose IV infusion of 10 mg/kg Process E belatacept and 10 mg/kg Process C belatacept
- To assess the immunogenicity of Process E belatacept and Process C belatacept.

3.3 Exploratory Objective

There are no exploratory objectives.

4 ENDPOINTS

4.1 Efficacy Endpoints

There are no planned efficacy endpoints.

4.2 Safety Endpoints

Safety endpoints include the occurrence of AEs, SAEs, and AEs leading to discontinuation; results of clinical laboratory tests, vital sign measurements, ECG findings, and physical examinations; and marked abnormalities in clinical laboratory test results.

4.3 Pharmacokinetic Endpoints

Pharmacokinetic parameters of belatacept will be derived from serum concentration versus time data by collection interval. Individual PK parameter values will be derived by noncompartmental methods by a validated PK analysis program using actual times.

The primary endpoints are Cmax and AUC(INF) of belatacept.

The secondary PK endpoints are Tmax, AUC(0-T), T-HALF, CLT, and Vss of belatacept.

Table 4.3-1: PK Parameters, Naming Conventions and Definitions

Parameter	Definition
Cmax	Maximum observed serum concentration
Tmax	Time of maximum observed serum concentration
AUC(0-T)	Area under the serum concentration-time curve from time zero to time of last quantifiable concentration
AUC(INF)	Area under the serum concentration-time curve from time zero extrapolated to infinite time
T-HALF	Terminal serum half-life
CLT	Total body clearance
Vss	Volume of distribution at steady state

4.4 Biomarker Endpoints

There are no planned biomarker endpoints.

4.5 Exploratory Biomarker Endpoints

There are no planned exploratory biomarker endpoints.

4.6 Immunogenicity Endpoints

The immunogenicity endpoint includes the incidence of anti-belatacept antibodies.

5 SAMPLE SIZE AND POWER

[REDACTED]

[REDACTED]

[REDACTED]

6 STUDY PERIODS, TREATMENT REGIMENS AND POPULATIONS FOR ANALYSES

6.1 Study Periods

The pre-treatment period will be from the time the Informed Consent Form (ICF) is signed until just prior to dosing on Day 1 for all subjects. The pre-treatment period will be no longer than 28 days and will include all screening, Day -1, pre-dose on Day 1 and randomization procedures.

Treatment period will be from the time of dosing on Day 1 until the subject is discharged on Day 71 (or until premature discontinuation after dosing on Day 1)

Any data collected at study discharge and afterwards will be assigned to the post-treatment period.

6.2 Treatment Regimens

Treatment A = belatacept 10 mg/kg IV, Process E belatacept

Treatment B = belatacept 10 mg/kg IV, Process C belatacept

6.3 Populations for Analyses

The exclusion of the subjects from Site 2 due to major protocol deviations is described in the footer of planned outputs in the Data Presentation Plan (DPP) as appropriate.

- The Enrolled Population includes all subjects who sign an ICF.
- The Randomized Population is a subset of the Enrolled Population including only subjects who were randomly assigned to a treatment. When using the Randomized Population, subjects will be presented in the treatment group they were randomly assigned to, even when the treatment they received was different.
- The Treated Population is a subset of the Enrolled Population including only subjects who received a dose of study medication. All analyses using the Treated Population will be presented by randomized treatment group, except in cases where information was available which indicated that a subject received a different treatment for the entire course of their participation in the study. In this case, the safety data and PK data for those subjects will be presented by the treatment actually received.

- The PK Population is a subset of the Treated Population. The PK population includes all treated subjects who had any available concentration-time data and did not have any protocol deviations which were determined to affect PK parameters.
- The Evaluable PK Population is a subset of the PK Population. The Evaluable PK Population includes all subjects who have adequate PK profiles. All available derived PK parameter values will be included in the PK data set and reported, but only subjects with adequate PK profiles will be included in the summary statistics and statistical analysis.
- The Immunogenicity Analysis Population: All treated subjects with at least 1 post-baseline immunogenicity result reported will be included in immunogenicity analysis.

